# 9. PROCEDURE

#### 9.1 Consent

Subjects will be given an informed consent form (ICF) to read and sign. They will have all of their study related questions answered by the Investigator or designated staff. Subjects who qualify based on the inclusion and exclusion criteria will be enrolled into the study.

## 9.2 Method of Application:

Occlusive – Test products to be studied under occlusive conditions will be applied on a 25-millimeter Hill Top Chamber®, consisting of an outer ring and an inner, flexible flange. Within the chamber is a non-woven Webril ® pad. The chamber is surrounded by a Durapore® semi-occlusive, hypoallergenic adhesive tape.

#### 9.3 Test Products:

The test product will be applied on the 25-millimeter Hill Top Chamber®, which will be applied directly to the test site. Enough product will be used to cover the chamber.

## Positive Control:

0.5% sodium lauryl sulfate (Sigma Chemicals, St. Louis, Missouri) in distilled water will be applied as a positive control. Positive control is applied on the same type of occlusive patch as the test product and is applied to the intrascapular region of the subjects' back. Positive control remains on the subjects' skin for 48 hours. The patch is removed, and the positive control site will be evaluated according to the Berger and Bowman Scale by a trained ALS staff member. Positive reactions are notated and reported in final report. Positive Control will only be applied for Induction 1.

#### Negative Control:

Distilled water will be applied as a negative control. Negative control is applied on the same type of occlusive patch as the test product and is applied intrascapular regions of the subjects' back. Negative control remains on the subject skin for 48-72 hours. The patch is removed and will be evaluated according to Berger and Bowman Scale by a trained ALS staff member. Positive reactions are notated and reported in final report. Subjects who observe a positive reaction are dropped from the study. The negative control will be applied throughout the entire study along with test product.

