#### 9.4 Test Product Preparation

Test Product Preparation will be performed as noted below unless otherwise requested by Sponsor. Prepare ColActive Plus Collagen Matrix Dressing samples using the following method:

Step 1: ColActive Plus Collagen Matrix Dressing: cut with sterile scissors to fit the chamber of the patch (25-millimeter diameter).
Step 2: Place the test article directly on the Hill Top Chamber®.
Step 3: 0.8mL of distilled water will be dispensed to saturate the test product.\*

Step 4: Place a Hill Top Chamber® on the test site.

\*Visual inspection will be done to confirm the entire test article has come in contact with distilled water and test product has transformed into a gel.

9.5 Test Sites/ Procedure:

The patches will be applied directly to the skin of the intrascapular regions of the back, to the right and/or left of the midline, and/or upper arms.

Subjects will be given a Panelist Instructions for the Safety Patch Test. Subjects will be dismissed with instructions to keep the test area dry while the patches are in place and to not expose the test area to direct sunlight. Subjects will be instructed to notify clinical staff during the course of the study should they begin using any new medications, cease taking any medications or have any change in their medical condition.

Patches will remain in place for a minimum of 48 hours. Subjects will be instructed to not remove the patches prior to their next scheduled visit. Subjects patched on Friday will have patches remain on until the following Monday (72 hours). The procedure will be repeated until a series of 9 consecutive 48-hour exposures have been made over 3 consecutive weeks. This is considered the induction phase.

Before each re-application, the test sites will be visually evaluated for any reaction.

Following the induction phase, subject will be given a minimum of 10-day rest period.

A challenge or test dose will be applied once to a previously unexposed test site. Clinical staff will remove the patches 48 hours post-application. Reactions will be scored 30 minutes post-removal, 24-hours post-removal, and 48-hours post-removal. The skin grader will be blinded to the treatment assignments and any previous scores.

Skin response to the test product will be evaluated according to the Berger and Bowman Scale (Section 8. Experimental Techniques and Methods).

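### Are the negative control and the test product read on different scales at challenge?

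*Protocol*

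**What the plan says.** Section 8 opens by naming the Berger and Bowman scale for the test product and then sets out two lists. The first is headed for the induction phase and carries the Berger and Bowman name. It has numeric scores 0 to 7 and its own letter grades. The second is headed for the challenge phase without that name. It has 0, +, 1, 2 and 3, with a different set of letters.

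Section 9.3, under Negative Control, says of the control site "The patch is removed and will be evaluated according to Berger and Bowman" (the word for scale follows). It adds "The negative control will be applied throughout the entire study along with test product" and "Subjects who observe a positive reaction are dropped from the study".

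Section 9.5 describes "a series of 9 consecutive 48-hour exposures" for induction and then "A challenge or test dose will be applied once to a previously unexposed test site". The challenge paragraph gives three reading times after removal (30 minutes, 24 hours and 48 hours) and states "The skin grader will be blinded to the treatment assignments and any previous scores". The next sentence reads "Skin response to the test product will be evaluated according to the Berger and Bowman", followed by the pointer "Scale (Section 8. Experimental Techniques and Methods". The re-challenge criterion later in Section 9.5 is limited to grades 1, 2 and 3.

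**The concern.** Read alone, the Negative Control paragraph ties a control worn in every phase to a scale that Section 8 labels as the induction scale. For the test product, Section 9.5 at least points to Section 8, where a challenge list can be found. The control paragraph has no such pointer. The apparent result is that at challenge the control site is scored 0 to 7 while the product site beside it is scored on the challenge list.

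The two lists are not interchangeable. Grade 1 is only just visible erythema on the induction list, but a mild pink on the challenge list. The + category exists only at challenge. The letter B means marked glazing on one list and a bulla on the other.

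If the split were real, two things would be at stake.

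- **Retention of subjects.** A positive control reaction removes the subject, and Section 10 leaves discontinued subjects out of the analysis unless the reason was related to the product. Faint erythema at the control site could be a numeric 1 on one list and a + on the other.
- **Blinding.** A grader who needs a different scale for the control site has to know which site it is.

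**Working it through.** No figure in the protocol depends on this point, so the check is a comparison of the text, followed by a bound on its reach.

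**Scale named for each article**

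| Article | Where | Scale named | Phase limit stated |
|---|---|---|---|
| Test product | Section 8, opening sentence | Berger and Bowman (reference 6) | none; it introduces both lists |
| Test product | Section 9.5, directly after the challenge reading times | Berger and Bowman (reference 6), pointing to Section 8 | none |
| Negative control | Section 9.3 | Berger and Bowman (reference 6) | none |
| Positive control | Section 9.3 | Berger and Bowman (reference 6) | applied at Induction 1 only, so no question arises |

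**Possible readings**

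1. The name stands for the whole of Section 8. Both articles then use the induction list in induction and the challenge list at challenge.
2. The name means only the list so headed. Both articles then use 0 to 7 throughout, and the challenge list is never used.
3. The name is literal for the control and loose for the product. Only this reading produces a split, and it gives the same words two meanings.

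**Which reading fits the rest of the protocol**

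- Section 8 is the only place where any scale is set out. Its headings are by phase, and neither list excludes control sites.
- The re-challenge criterion names grades 1, 2 and 3 only. On the challenge list these are all the numeric grades above +. On the 0 to 7 list the criterion would leave out grades 4 to 7, the strongest reactions. This supports reading 1 over reading 2.
- The grader is blinded to treatment assignments at the challenge readings. That fits one scale for all sites at a visit and does not fit reading 3.
- The wear time given for the negative control is 48 to 72 hours. The 72-hour wear belongs to patches applied on a Friday, whereas challenge patches come off at 48 hours. The sentence on grading the control may therefore have been written with induction in mind. This is suggestive, not conclusive.

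**Reach, if reading 3 were followed all the same**

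- Control applications per subject: 9 induction + 1 challenge = 10. Affected: 1/10 = 10%, plus any re-challenge.
- Control readings per subject at challenge: 1 if read only at removal, 3 if read at all three post-removal times (assumption).
- Weight of one dropped subject: 1/50 = 2.0% of the minimum number, or 1/75 = 1.3% of the approximate enrolment. This is the weight of any single loss and does not measure a scale effect.
- Expected number of drops due to the choice of scale: not estimable. The protocol gives neither a reaction rate to distilled water nor the grade that counts as positive. The number may be zero.

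**Faint reactions**

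The closing paragraph of the Section 8 scales treats barely visible or minimal reactions, and the + grade, as inconclusive and leaves them out of calculation. Grade 1 on the induction list is described in those same terms. The paragraph follows the challenge list and speaks of calculation, not of dropping subjects, so it does not settle the matter. It is, however, the only rule on faint reactions, and it treats the two descriptions alike.

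**The case for a change.** The best case for a change is that the naming really is inconsistent and would cost only a few words to correct. Reading 1 stretches the Berger and Bowman name over a list that does not carry it, and reading 2 leaves a whole list unused, so on either reading some sentence is inaccurate. The negative control is also the only control for which the label reaches challenge, and its paragraph lacks the pointer to Section 8 that the product has. A control reading has a consequence for the subject, and the grade that counts as positive is not given.

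The inconsistency stands, as does the fact that the two lists are not equivalent. Both apply equally to product and control. The missing pointer carries little weight, because a reader looking for any scale can only go to Section 8 and there meets a heading for each phase. The blinding argument depends on the split: without it, the blinding statement is evidence for a single scale. The argument about dropped subjects needs the split and also an assumed threshold for a positive reaction. That undefined threshold is a separate question, which relabelling the scale would not answer.

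**Conclusion.** The concern does not hold as a fault in the plan. The protocol does not assign different scales to the negative control and the test product: it gives both the same name and the same reference. The phase headings in Section 8, the grade range in the re-challenge criterion and the blinded grader together lead a sensible site to use the challenge list for every site at challenge and re-challenge.

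What is left is a clerical slip. Berger and Bowman is named without regard to phase in Sections 8, 9.3 and 9.5, while only the induction list bears that heading. The slip bears on 1 of 10 scheduled control applications per subject. It has no demonstrable effect on any reported result, and correcting the label would not be expected to change one.

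This conclusion assumes that challenge score sheets follow the Section 8 headings. If a site did score control sites on 0 to 7 at challenge, the effect would depend on a threshold and a reaction rate that the protocol does not give.

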## **10. SUBJECT DISCONTINUATION**

The removal of a study subject by the Principal Investigator could occur due to the following reasons:

- 1. Adverse Event
- 2. Concomitant treatments or illnesses incompatible with the study

- 3. Withdrawal of consent by the participant
  - a. All subjects will be informed of the fact that they may, of their own free will, withdraw their consent to participate in the study, if they so wish.
- 4. Loss of follow-up
- 5. Emergence of a non-inclusion criterion
- 6. Researchers' decision
- 7. Protocol violation

Those subjects who, for some reason, are discontinued from the study will not be replaced. Data from these subjects will not be analyzed unless the reason for their discontinuation was related to the investigational product. The Investigator should carefully track and document all premature discontinuations and their reasons on study documentation and also, when necessary, on the "adverse event" form, as well as on the study documentation.

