# **14. DATA REPORTING**

Skin responses to the test product for each subject will be presented in a table in the final report. Product reporting for skin irritation will be based on scores after the first 48hour patch removal. Product reporting for skin sensitization (contact allergy) will be based on scores after the 72hour patch removal of challenge phase.

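### Dropping distilled-water reactors and then not analysing their data removes first-patch irritation scores recorded while the water site was still negative

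*Protocol*

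**What the plan says.** Four parts of the protocol bear on this.

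- **Section 9.3, Negative Control.** Distilled water is worn beside the product: "The negative control will be applied throughout the entire study along with test product". For a positive reaction at that site the rule is "Subjects who observe a positive reaction are dropped from the study", and the reaction itself is disclosed: "Positive reactions are notated and reported in final report". No score threshold is given for a positive reaction.
- **Section 10, Subject Discontinuation.** Discontinued subjects are not replaced, whatever the reason, and "Data from these subjects will not be analyzed unless the reason for their discontinuation was related to the investigational product".
- **Section 14, Data Reporting.** "Product reporting for skin irritation will be based on scores after the first 48hour patch removal". The same section promises a listing: "Skin responses to the test product for each subject will be presented in a table in the final report".
- **Section 9.5.** Sites are evaluated before every re-application during nine induction exposures. A single challenge patch follows, read 30 minutes, 24 hours and 48 hours after removal.

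**The concern.** A reaction to a water patch is, on its face, not product-related. Section 10's default therefore applies to a subject dropped under the Negative Control rule, and all of that subject's product-site scores leave the analysis. The irritation endpoint is fixed at the first patch, but the drop can be triggered at any later patch. A subject whose product and water sites were both scored at the first removal, with the water site negative, has a first-patch score that is sound by the control's own logic. If the water site reacts at, say, the seventh patch, that score is excluded because of something that happened afterwards.

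The exclusion may also not be neutral. The two sites share the patch system ("Negative control is applied on the same type of occlusive patch as the test product") and the wetting agent ("0.8mL of distilled water will be dispensed to saturate the test product"), and Section 11 names tape reactions as a risk. It is plausible, though not documented, that subjects who react at the water site also react more often at the product site. If they do, removing them lowers the irritation summary in data meant for a regulatory submission. If they do not, nothing is biased, but valid scores are still discarded.

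**Working it through.** The protocol states no reaction rate, so there is no figure to reproduce. The check has a textual part and an illustrative part.

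**Text, by timing of the first water-site reaction**

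- *At the first removal.* The product patch comes off at the same visit, so a first-patch product score is likely. It is not strictly guaranteed, because Section 9.5 ties evaluation to re-application and this subject has none. The score comes from the same patch as the control reaction, so its interpretation is open.
- *At induction patches 2 to 9.* The first-patch score was recorded before re-application, with the water site negative. Section 10 excludes it by default. There is no challenge score to lose.
- *At challenge.* The first-patch score was recorded with the water site negative and is excluded by default. Challenge readings taken up to the drop are excluded too; a subject dropped at the 30-minute reading may have no later ones.

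No passage keeps scores obtained before the drop.

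**Illustration for irritation**

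Inputs: N = 75 (Section 6). Assumed: c, the share dropped for a water reaction; r1, their first-patch product-site reaction rate; r0, the rate in everyone else; d = r1 − r0.

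- Rate in all enrolled = c·r1 + (1 − c)·r0
- Rate with dropped subjects excluded = r0
- Gap = c·d

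If the first water reaction is equally likely at each of the 10 patches (9 induction plus 1 challenge, assumed), 0.9 of the dropped subjects had a negative water site at the first patch.

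| c | Dropped, 75c | Water site negative at patch 1, 0.9 × 75c | Gap, d = 0 | Gap, d = 20 points | Gap, d = 40 points |
|---|---|---|---|---|---|
| 2% | 1.5 | 1.35 | 0 | 0.4 | 0.8 |
| 5% | 3.75 | 3.38 | 0 | 1.0 | 2.0 |
| 10% | 7.5 | 6.75 | 0 | 2.0 | 4.0 |

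Gaps are in percentage points. The largest, 4.0 points, is 75 × 0.04 = 3 subjects. The gap pools early and late control reactors, because nothing in the protocol supports separate values of d. Wider assumptions give wider answers: c = 20%, r1 = 60% and r0 = 2% give 0.20 × 58 = 11.6 points.

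**If the product-related exception is used**

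Suppose Section 10's exception kept every dropped subject who had a product-site reaction and excluded the rest. The analysed rate becomes [c·r1 + (1 − c)·r0] / [c·r1 + (1 − c)]. With c = 10%, r0 = 2% and r1 = 42% (assumed), that is 0.060 / 0.942 = 6.4%, against 6.0% in all enrolled. The summary would then be slightly too high, so the direction depends on how the exception is applied.

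**Illustration for sensitization**

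Only subjects whose first water reaction occurs at challenge can have an excluded challenge score. Under the equal-chance assumption:

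- Number: 75c / 10 = 0.15, 0.375 and 0.75 subjects for c = 2%, 5% and 10%.
- Share of those reaching challenge: (c/10) / (1 − 0.9c) = 0.20%, 0.52% and 1.10%.
- Gap at a 40-point difference: 0.08, 0.21 and 0.44 points.

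**The case against.** The strongest reply is that excluding people who react to water under the same patch is a recognisable validity rule. Their product-site score cannot readily be credited to the product, and the objective in Section 2 is the product's own potential. Measured against a product-attributable rate, keeping them could bias the result upward. This stands for scores from the same patch as the control reaction, where the choice of main set is a genuine trade-off. It does not reach a first-patch score taken while the water site was negative, because the control gave no reason to doubt that score.

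Four further points stand.

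- Section 14 defines no irritation percentage, denominator or test, so the gap above is in a summary that the protocol does not spell out.
- All the rates are assumed, and the range includes zero.
- Section 10's exception may be judged to cover subjects who react at both sites, and its list of reasons does not name a control reaction. The general wording about discontinuation for any reason still makes exclusion the natural default.
- With no threshold for a positive water reaction, the number of subjects affected cannot be determined.

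A reader might infer that the scores vanish from the report. The documents do not support that: control reactions are reported and Section 14 tabulates responses for each subject. A listing is not inclusion in the analysis, however, and the protocol does not say whether dropped subjects appear in the table.

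Nor can the point be left to a statistical analysis plan as a missing detail, because the protocol itself states the exclusion rule.

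**Conclusion.** The point holds in a limited form. Read together, Sections 9.3 and 10 exclude by default all product-site scores of a subject dropped for a distilled-water reaction. These include first-patch irritation scores recorded before that reaction, from subjects who are not replaced.

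A reader might go further and conclude that the plan understates irritation. The documents do not support that. The bias is zero if control and product reactions are unrelated. The summary is too low if control reactors react more at the product site and are excluded, and it could move the other way depending on how the product-related exception is used. Under the assumed range (c = 2% to 10%, difference 0 to 40 points) the shortfall is 0 to 4 points, or 0 to 3 of 75 subjects. These are rates of any product-site reaction, not of product-attributable reactions.

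A reader might also extend the point to sensitization. The effect there is negligible: fewer than one affected subject and at most about 0.4 points on the same assumptions, since subjects dropped in induction have no challenge score.

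Nothing here bears on whether dropping control reactors is the right conduct rule.

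**What to change.** Leave the Negative Control conduct rule in Section 9.3 unchanged and add to Section 10 wording such as:

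*For subjects dropped because of a negative-control reaction, product-site scores obtained before the first such reaction, including the first-patch irritation score, are retained in the analysis. Product-site scores from the same patch as the control reaction are listed as within-subject pairs with the control score, and the irritation summary is presented both with and without those subjects.*

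Also reconcile Section 10 with Section 14 by stating that the table of responses for each subject includes dropped subjects.

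The cost is a short addition to Section 10, a clarification in Section 14 and one extra table, with no added visits or patches. The downside is that a few possibly non-specific reactions will appear, each shown beside its control score. Settling this before scores are known avoids choosing the analysis set after seeing them.

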#### 9.4 Test Product Preparation

Test Product Preparation will be performed as noted below unless otherwise requested by Sponsor. Prepare ColActive Plus Collagen Matrix Dressing samples using the following method:

Step 1: ColActive Plus Collagen Matrix Dressing: cut with sterile scissors to fit the chamber of the patch (25-millimeter diameter).
Step 2: Place the test article directly on the Hill Top Chamber®.
Step 3: 0.8mL of distilled water will be dispensed to saturate the test product.\*

Step 4: Place a Hill Top Chamber® on the test site.

\*Visual inspection will be done to confirm the entire test article has come in contact with distilled water and test product has transformed into a gel.

9.5 Test Sites/ Procedure:

The patches will be applied directly to the skin of the intrascapular regions of the back, to the right and/or left of the midline, and/or upper arms.

Subjects will be given a Panelist Instructions for the Safety Patch Test. Subjects will be dismissed with instructions to keep the test area dry while the patches are in place and to not expose the test area to direct sunlight. Subjects will be instructed to notify clinical staff during the course of the study should they begin using any new medications, cease taking any medications or have any change in their medical condition.

Patches will remain in place for a minimum of 48 hours. Subjects will be instructed to not remove the patches prior to their next scheduled visit. Subjects patched on Friday will have patches remain on until the following Monday (72 hours). The procedure will be repeated until a series of 9 consecutive 48-hour exposures have been made over 3 consecutive weeks. This is considered the induction phase.

Before each re-application, the test sites will be visually evaluated for any reaction.

Following the induction phase, subject will be given a minimum of 10-day rest period.

A challenge or test dose will be applied once to a previously unexposed test site. Clinical staff will remove the patches 48 hours post-application. Reactions will be scored 30 minutes post-removal, 24-hours post-removal, and 48-hours post-removal. The skin grader will be blinded to the treatment assignments and any previous scores.

Skin response to the test product will be evaluated according to the Berger and Bowman Scale (Section 8. Experimental Techniques and Methods).

The Sponsor will be notified within 1-2 business days of any subject who: •exhibits an erythema score of 2 or greater •exhibits papules, vesicles, bullae and/or spreading beyond the patch site, regardless of the degree of erythema •requires follow-up

If any subject exhibits a grade 2 during induction phase, the test site will be changed. If the subject shows another grade 2 of the same test product during induction phase at the new test site, the test product will be discontinued for safety concerns. If any subject shows a grade 3 or greater during induction phase, the test site will be discontinued for safety concerns.

If any subject shows a significant reaction at the 30 minutes post-removal, 24-hours post-removal, or 48-hours post-removal evaluation during the challenge phase (Grade 1, 2, and 3 only), the Investigator may decide to schedule a re-challenge patch test for confirmatory purposes. This follow-up investigation will be conducted approximately 4-8 weeks after the completion of the challenge phase and will be identical to the challenge phase.

In the event of a re-challenge patch the original test substance should be applied under the same testing conditions (concentration and patch type) to confirm delayed contact hyper-reactivity. Related substances (product reformulations, individual ingredients, ingredient groups, etc.) can also be applied to aid in determining the causative relationship but must be pre-approved prior to application.

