#### Induction Phase (Berger and Bowman1 Scale)

## Numeric Scores

- 0 = No evidence of irritation
- 1 = Minimal erythema, barely perceptible
- 2 = Moderate erythema, readily visible; or minimal edema; or minimal papular

response

- 3 = Strong erythema; or erythema and papules
- 4 = Definite edema
- 5 = Erythema, edema and papules
- 6 =Vesicular eruption
- 7 = Strong reaction spreading beyond test site

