## **11. ADVERSE EVENTS**

The most commonly observed reactions in this study are:

1. Itching, redness, rash, peeling, swelling and in rare cases blistering.

2. There is also a possibility of getting a reaction from the tape possible resulting in hyperpigmentation.

There also may be risks and discomforts, which are not yet known.

An adverse event (AE) is any unfavorable medical occurrence experienced by the subject, whether or not the event may be related to the test article.

Each adverse event must be promptly recorded and sufficiently documented by the Study Director in the source documentation and case report form even if the adverse event is assessed by the Study Director as unlikely to be related to the study. Adverse events are graded on a scale of severity (mild, moderate, severe, or lift threatening) and on a scale of relationship to the product (unknown, unrelated, unlikely, possible, probable, or definite). All adverse events will be reported to the Sponsor within five business days. All adverse events will be followed up until resolved, stabilized, the subject is lost to follow-up or the event is otherwise explained. All follow-up information should be reported to the Sponsor.

A serious adverse event (SAE) as defined in the CFR 312.32 is "any experience that is fatal or life threatening, is permanently disabling, requires inpatient hospitalization, or is a congenital anomaly, cancer, or overdose". All serious adverse events will be reported to the Sponsor within 24 hours of ALS Beauty & Personal Care notification.

If, according to the Investigator, medical care is warranted, appropriate referrals will be made. ALS Beauty & Personal Care will follow adverse events until resolution.

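### The no-removal rule for patches in Section 9.5 has no written exception for a marked reaction; adding one would be a modest safety improvement

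*Protocol*

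**What the plan says.** **Wear rule (Section 9.5).** "Subjects will be instructed to not remove the patches prior to their next scheduled visit". The minimum wear is 48 hours, and Friday patches stay on until Monday, 72 hours. Induction sites are inspected before each new application. For the challenge, "Clinical staff will remove the patches 48 hours post-application". A re-challenge, if scheduled, takes place about 4 to 8 weeks after "completion of the challenge phase and will be identical to the challenge phase".

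**Stopping rule (Section 9.5, same section).** "If any subject shows a grade 3 or greater during induction phase, the test site will be discontinued for safety concerns". A first grade 2 moves the site, and a second grade 2 at the new site stops the product.

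**Scale and expected reactions (Sections 8 and 11).** The induction scale runs from 0 to 7 and includes "4 = Definite edema", vesicular eruption at 6, and "7 = Strong reaction spreading beyond test site". Section 11 gives the commonest reactions as "Itching, redness, rash, peeling, swelling and in rare cases blistering".

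**Controls (Section 9.3).** The 0.5% sodium lauryl sulfate positive control is worn for 48 hours, at the first induction application only. The distilled-water negative control is worn for 48 to 72 hours throughout the study. Both use the same type of occlusive patch as the test product.

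**Related safeguards.** Subjects are to tell staff if they "have any change in their medical condition" (Section 9.5). Section 10 allows withdrawal at will, and removal by the investigator for an adverse event or by the researchers' decision. Section 11 provides for referral when medical care is needed. Subjects also receive a separate panelist instruction sheet, which is not at hand.

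**The concern.** The protocol treats a grade of 3 or more in induction as a reason to stop exposing that site. The only scheduled moment at which the grade is assigned is the visit at which the patch comes off. Between visits, the one specific instruction that the protocol gives the subject about a patch is to leave it on. It names no symptom that should lead to early removal, although Section 11 foresees swelling and, rarely, blistering.

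The stake is mainly subject safety: exposure under occlusion may run longer than it needs to at a site that is already reacting strongly. A smaller stake is the reading of the scores. Section 14 bases irritation reporting on the first 48-hour patch, and Section 9.5 times the challenge readings from removal. If a patch does come off early, the time and reason have to be on record for the score to be interpreted. The text does not ask for either.

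**Working it through.** No sample size, power or error rate is involved, and the plan gives no figure on this point to reproduce. The check sets the provisions side by side.

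1. **Does the protocol state an exception?** The wear rule, the stopping rules, Sections 10 and 11 and the two questionnaires in the appendices were read for one. None tells a subject that a single patch may come off early because of a reaction. The recruitment questionnaire (Appendix I) asks only whether the subject is willing to wear the patches as instructed.

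2. **Can the stopping rule act while a patch is on?** It needs a grade. Scheduled induction grading happens before each re-application, that is, at the visit. So on the schedule as written it acts only after removal.

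3. **Do the foreseen reactions reach the threshold?** The threshold is grade 3 or higher.
   - Swelling: grade 4 if the edema is definite (4 ≥ 3, reached); grade 2 if it is minimal (2 < 3, not reached).
   - Blistering, read as vesicular eruption: grade 6 (reached).
   - A strong reaction spreading beyond the site: grade 7 (reached).
   - Grade 3 itself, strong erythema or erythema with papules, also triggers the rule.

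4. **How long could such a site stay covered?** Let W be the planned wear and t the hours from application until the reaction becomes marked. The remaining occlusion is W − t.
   - Weekday patch, W = 48: at most 48 hours.
   - Friday patch, W = 72: at most 72 hours.
   - The protocol does not give t. As an illustration only, t = 24 leaves 48 − 24 = 24 hours or 72 − 24 = 48 hours. The full range runs from 0 up to W.

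5. **Which patches are concerned?** The wear rule is general, so it covers the test product and both controls. The sodium lauryl sulfate patch is the one meant to irritate. It is worn once for 48 hours, so the stopping rule has no later application of it to prevent, and early removal would be the only way to shorten that exposure.

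6. **Challenge and re-challenge.** The induction stopping grades do not apply there, so the comparison in steps 2 and 3 is confined to induction. The wear question is the same, however: 48 hours with removal by staff and no early-removal provision. A re-challenge patch may go to a subject who has already shown a significant challenge reaction, which makes a clear instruction more useful there.

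7. **How many subjects?** This cannot be computed, because the document gives no rate of marked reactions.

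**The case against.** The strongest reply is that the protocol already leaves a route open. The instruction restrains the subject, not the staff, and the sentence on challenge removal describes the normal course without forbidding an earlier one. A subject who reports a painful site can be called in and the patch taken off without breaching any sentence. Subjects must report a change in their condition, may withdraw at will, and may be removed for an adverse event. The panelist sheet, and the consent text that Section 7 says describes risks, are natural places for a line telling the subject to call, and neither can be read here. All of this stands, and it limits the weight of the point. It does not remove the point: the reporting duty does not mention patch-site symptoms, the withdrawal routes end participation when one patch may be all that needs to come off, and none of them qualifies the wear instruction.

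A reader might infer that the wear rule contradicts the stopping rule. It does not. The stopping rule prevents further exposure of a site already graded and makes no promise of monitoring under an occlusive patch. Exposure for 48 to 72 hours, read at a visit, is the method of the test.

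A reader might also see particular danger in the fish-derived collagen, because only a known fish allergy is excluded (Section 6.2). The document gives no rate for unrecognised allergy, and allergic symptoms would already fall under the duty to report. Nor does counting the planned patches say anything about harm.

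Two practical objections stand and shape the fix. A subject cannot see blistering under a chamber, or spreading on the back, so the triggers should be symptoms that the subject can notice. And shortened exposures complicate the scores, so the removal time must be recorded.

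**Conclusion.** The point holds as a modest safety improvement. Read literally, the wear instruction lets a site that would be discontinued on grading stay occluded until the next visit, for at most 48 hours, or 72 hours over a weekend.

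This rests on the protocol alone. It assumes a subject who takes the instruction at its word and does not call, and it does not assume that staff would refuse an early removal. It would be wrong to conclude that the trial has no early-removal provision: the panelist sheet or the consent text may contain one. If either does, the remaining task is to make Section 9.5 agree with it. No planned analysis is shown to be wrong, and the number of subjects who would be affected is unknown.

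**What to change.** Add to the wear instruction in Section 9.5, for all patches (test product, sodium lauryl sulfate positive control and negative control) in induction, challenge and re-challenge:

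> *except that a subject with severe pain or burning, noticeable swelling, or allergic symptoms contacts staff at once and the patch is removed early on staff advice, or immediately by the subject if severe; the site is scored at an unscheduled visit and the time and reason for removal are recorded.*

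Then check the Panelist Instructions and align them with this wording. Adverse events are recorded and graded under Section 11 as now.

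The cost is one sentence, a check of the sheet, and the written approval and IRB submission that Section 12 requires for any protocol change. In conduct, expect a few shortened exposures and occasional unscheduled visits. If the first induction patch is the one removed early, that subject's irritation score comes from less than 48 hours of wear; the recorded removal time makes this visible when the scores are read. Subjects without such symptoms keep the 48- or 72-hour wear unchanged.
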